20.4 INTERIM REPORTS

An interim database lock will be performed for preoperative data after completion of the second preoperative visit.

20.5 SAMPLE SIZE CALCULATIONS

The sample size determination is based on the primary endpoint of uncorrected distance visual acuity (UCDVA). There is 90% power to detect a 1-line or greater difference in mean UCDVA between the treatment and control groups with 55 subjects in each group. This assumes one-sided two-sample t-test with an alpha of 0.05 and standard deviation of 1.6 lines. Adding 20% screen failure/drop-out rate will require enrolling 69 subjects per group.

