- Mean MRSE at 4 months postoperative compared to target MRSE
- Percent of eyes with MRSE within 0.50 D and within 1.00 D of target MRSE at 4 months postoperative
- Contrast acuity at 4 months postoperative compared to 3-month.
- Mean change in total meibomian gland score from 3 months to 4 months postoperative.
- Mean change in total SPEED score from 3 months to 4 months postoperative.
- Rates of adverse events in the Study and Control groups.
- Rates of medical and/or lens findings in the Study and Control groups.

STUDY VISITS AND PROCEDURES:

Inclusion and exclusion qualifications will be assessed at the start of Preoperative Visit #1 according to the protocol criteria. The Informed Consent Document and Authorization for Use/Disclosure of Health Information form (HIPAA authorization) must be signed by any subjects who agree to participate in the study prior to undergoing any study-specific procedures. After determination that all inclusion/exclusion criteria have been met, enrolled subjects will be randomized to either Study group or Control group in a 1:1 ratio.

Study visit schedule, procedures and key data collected at each visit are shown in **Appendix A, Appendix B, and Section 10.2, Visit Schedule, Table 1.**

DATA ANALYSIS:

Key study endpoints are the comparisons between study group and control group for precision of biometric measurements preoperatively, mean change in total Meibomian gland score at 1 month postoperatively, mean monocular UCDVA at 3 months postoperatively, rate of refractive predictability at 3 months postoperatively and rate of directed reported ocular symptoms at 3 months postoperatively. Additional endpoints will be evaluated at 1 and 3 months postoperatively for the both groups and 4 months postoperatively for crossover Control group.

Visual acuity data will be converted to LogMAR values prior to analysis. Comparisons between study group and control group for the mean monocular UCDVA at 3 months postoperatively will be performed using one-sided two-sample t-tests with alpha set at 0.05. Precision of preoperative biometric measurements is defined as the average of the three computed standard deviations from each preoperative visit. The Study group is expected to have better total Meibomian gland score at 1 month postoperatively compared to the Control group, and to have better

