20.1 ANALYSIS POPULATION

The primary study population will be all eyes that are randomized for precision of biometric measurements, and all eyes that are randomized and implanted for all other analyses. Mean change in total Meibomian gland score will be compared between study group eyes and control group eyes at 1 month postoperatively. All other key study endpoints will be evaluated at 3 months postoperatively. Additional endpoints will be evaluated at 1 month and 3 months postoperatively for the study group and control group and 4 months postoperatively for crossover control group only. Missing data will not be imputed.

Since both eyes of the same subject will be randomized into the same group, eye-specific measurements of same subject are clustered and likely to be positively correlated. As a subset analysis, right and left eyes of subjects will be analyzed for the key eye-specific study endpoints separately to assess for any differences by eye. Demographics/enrollment/accountability data and binocular data will be reported for all randomized subjects with study IOLs successfully implanted..

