#### 2 ANALYSIS POPULATIONS

#### 2.1 ANALYSIS POPULATIONS

The primary analysis population will be all eyes that are randomized for the precision of biometric measurements, and all eyes that are randomized and implanted for all other analyses. Mean change in total Meibomian gland score will be compared between study group eyes and control group eyes at 1 month postoperatively. All other key study endpoints will be evaluated at 3 months postoperatively. Additional endpoints will be evaluated at 1 month and 3 months postoperatively for the study group and control group and 4 months postoperatively for crossover control group only. Missing data will not be imputed.

Since both eyes of the same subject will be randomized into the same group, eye-specific measurements of same subject are clustered and likely to be positively correlated. As a subset analysis, right and left eyes of subjects will be analyzed for the key eye-specific study endpoints separately to assess for any differences by eye. Demographics/enrollment/accountability data and binocular data will be reported for all randomized subjects with study IOLs successfully implanted.

Version 1.0 1 SAP/DRYE-102-SELF

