#### 5 SAMPLE SIZE CALCULATIONS

The sample size determination is based on the primary endpoint of uncorrected distance visual acuity (UCDVA). There is over 90% power to detect a 1-line or greater difference in mean UCDVA between the treatment and control groups with 55 subjects in each group. This assumes one-sided two-sample t-test with an alpha of 0.05 and standard deviation of 1.6 lines. Adding 20% screen failure/drop-out rate will require enrolling 69 subjects per group.

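### The protocol's 90% power for 55 subjects per group does not follow from its own inputs: a one-sided 0.05 t-test gives 94.7%, and 90% needs only 45 per group

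*Protocol*

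**What the plan says.** Protocol section 20.5 sizes the trial on uncorrected distance visual acuity (UCDVA) and states: "There is 90% power to detect a 1-line or greater difference in mean UCDVA between the treatment and control groups with 55 subjects" (per group). The next sentence gives the basis: "This assumes one-sided two-sample t-test with an alpha of 0.05 and standard deviation of 1.6 lines". The synopsis repeats both sentences under its sample size heading.

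The one-sided label is not confined to the sizing paragraph. The synopsis, under data analysis, says that the 3-month comparison of mean monocular UCDVA "will be performed using one-sided two-sample t-tests with alpha set at 0.05".

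SAP section 5 carries the same difference, SD, test, alpha and group size, but words the result differently: "There is over 90% power to detect a 1-line or greater difference in mean UCDVA".

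The success criterion in protocol section 20.2 and SAP section 4.1.1 is p ≤ 0.05, with no statement of sidedness.

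**The concern.** Every input to the power calculation is stated, so the result can be recomputed with no judgement involved, and the protocol's figure does not come out. The protocol and SAP also describe the same calculation in different terms.

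The reader is left unsure whether the power or the sidedness is wrong. This matters a little more because the success criterion leaves sidedness unstated, so the sizing paragraph is one of the few places that fixes it, and its power figure fits the other reading. The stake is the accuracy and internal consistency of the record. The trial is not underpowered on its stated inputs.

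**Working it through.** **Inputs** (protocol section 20.5 and synopsis; SAP section 5 agrees)

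- Difference: 1 line
- SD: 1.6 lines
- Group size: n = 55 subjects per group, allocated 1:1
- Test: two-sample t-test, one-sided, alpha 0.05
- Stated power: 90%

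**Step 1: the plan's figure on its stated inputs**

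- Standardised effect: d = 1/1.6 = 0.625
- Degrees of freedom: 2 × 55 − 2 = 108
- Noncentrality: d × √(n/2) = 0.625 × √27.5 = 3.278
- One-sided 0.05 critical value of t on 108 df: 1.659
- Power = P(noncentral t with 108 df and noncentrality 3.278 exceeds 1.659) = **94.65%**

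The stated 90% is not reproduced. The type II error is 5.3%, where the protocol implies 10%.

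**Step 2: the group size that gives 90% on the stated inputs**

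| n per group | Power, one-sided 0.05 |
|---|---|
| 44 | 89.68% |
| 45 | 90.27% |
| 55 | 94.65% |

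**Step 3: could method or rounding explain the gap?**

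- Normal approximation: power at 55 is Φ(3.278 − 1.645) = 94.9%. The size for 90% is 2 × (1.645 + 1.282)² × 1.6² = 43.8, so 44.
- SD rounded to 1.6: an SD of 1.55 gives 95.7% and an SD of 1.65 gives 93.5%. Reaching 90% at 55 would take an SD of about 1.78 lines, which does not round to 1.6.
- Drop-out: 55/(1 − 0.20) = 68.75, so 69 per group. This agrees with the documents, so the mismatch lies only in the power statement.

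**Step 4: what does reproduce 90% at 55?**

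| n per group | Power, two-sided 0.05 |
|---|---|
| 54 | 89.58% |
| 55 | 90.12% |

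Under a two-sided 0.05 test (critical value 1.982), 55 is exactly the smallest size that reaches 90%. Put the other way, the one-sided alpha that gives 90% at 55 per group is 0.0246, about half the stated 0.05.

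**The case against.** The arithmetic is not in dispute. The case on the other side is about weight and about the remedy.

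- **Power as a floor.** Sponsors often quote the power target and not the achieved value. On the stated inputs 55 per group does deliver at least 90%, and the SAP says so correctly. This softens the point but does not remove it: the protocol states 90% flatly where the SAP says it is exceeded. A floor reading also does not explain why the chosen size is exactly the two-sided minimum and 10 per group above the one-sided one.
- **The two-sided origin is inference.** This stands. Every place that states sidedness says one-sided, and nothing describes a two-sided calculation. The explanation is offered only as the likely cause.
- **The label could be the wrong item.** Only the sponsor's sizing record can settle that. As written, however, the one-sided statements agree with one another in both documents, and the power figure is the item that does not fit.
- **94.7% is not the power of the planned eye-level comparison.** This also stands. SAP section 2.1 analyses "all eyes that are randomized and implanted for all other analyses", and protocol section 20.1 accepts that "eye-specific measurements of same subject are clustered and likely to be positively correlated". The documents do not say whether 1.6 lines is the SD of an eye or of a subject. If it is an eye-level SD and the two eyes of each subject are averaged, the SD becomes 1.6 × √((1 + ρ)/2). With an assumed between-eye correlation ρ, one-sided power at 55 subjects is 98.3% for ρ = 0.5, 97.0% for ρ = 0.7 and 94.65% for ρ = 1. None of these is 90%. The corrected figure should therefore be labelled as subject level.

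**Conclusion.** The stated power is wrong as written. On the protocol's own inputs it is understated by about 4.7 percentage points (94.65% against 90%), and 90% would need 45 per group, not 55. The result assumes the subject as the unit, as the sizing text does, with equal groups and the stated difference, SD, test and alpha. It does not depend on the choice between exact and approximate methods.

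The error runs in the safe direction. The comparison with 45 per group shows the size of the discrepancy and is not an argument for enrolling fewer subjects. This is a minor correction of the text.

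**What to change.** In protocol section 20.5 and in the sample size paragraph of the synopsis, replace the stated 90% with about 95% (94.7%) for 55 evaluable subjects per group. Keep the one-sided test, alpha 0.05 and SD of 1.6 lines. Add a short note that the figure is calculated at subject level, whereas the planned comparison of monocular UCDVA is on eyes. The minimum acceptable change is to say that power exceeds 90%, which also brings the protocol into line with the SAP. SAP section 5 needs no change.

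When making the edit, the sponsor should check the original sizing record to confirm which sidedness was used. An optional consistency edit, separate from this error, is to add the word one-sided beside p ≤ 0.05 in protocol section 20.2 and SAP section 4.1.1.

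The cost is wording in two protocol places. No extra subjects are needed, and the test, alpha and enrolment target stay as they are. If no further protocol revision is planned, the correct power can be given in the study report.

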APPENDIX A DIAGRAM OF STUDY FLOW

APPENDIX B SUMMARY OF PROCEDURES REQUIRED AT EACH VISIT

Examination	Preop Visit #1	LF Tx ^d (Study Group Only)	Preop Visit #2 ^e	Operative	1-Mo. Post-op	3-Mo. Post-op and Crossover LF Tx ^f	4-Mo. Post-op (Crossover Group Only)
Informed consent, medical and ocular history, inclusion/exclusion criteria	X						
Potential visual acuity, targeted refraction, IOL power calculations, corneal topography	X		X				
IOL power/serial number, Toric power/axis (if needed)				X			
Monocular UCDVA, BCDVA	X ^c				X	X	X
Binocular UCDVA, BCDVA					X	X	X
Binocular UCIVA and UCNVA						X	X
Manifest refraction	X ^c				X	X	X
Contrast acuity testing (binocular, 10% contrast acuity and 20/40 contrast threshold)						X	X
Keratometry, biometry (repeat 3 sets of biometry / keratometry measurements)	X		X				
Meibomian gland assessment	X				X	X	X
Ocular surface staining	X		X		X		
TBUT	X		X		X		
Eyelid margin evaluation	X		X		X		
Meibomian gland imaging (LipiScan or LipiView II)	X				X		X
Biomicroscopic slit-lamp exam ^a	X	X	X		X	X	X
Fundus exam ^b	X						
Adverse events	X	X	X		X	X	X
Ocular and systemic medications	X	X	X		X	X	X
Ocular/Visual symptom assessment (non-directed)	X		X		X	X	X
SPEED and PRVSQ questionnaires	X		X			X	X

^a Includes determination of medical and lens findings/complications, lens orientation. Slit-lamp exam is performed both before and after LipiFlow treatment.

^b Fundus exam may be performed dilated with ophthalmoscopy or undilated per site practice standard of care.

^c Preoperative UCDVA, BCDVA and refraction tests will be performed per site practice standard of care.

^d Preoperative LipiFlow treatment can occur the same day or within 1 week of Preoperative Visit #1.

^e Preoperative Visit #2 will be 2-4 weeks after LipiFlow treatment for study group and be 2-4 weeks after the Preoperative Visit #1 for control group.

^f LipiFlow treatment after 3 months postop exams for the Crossover Control group only.

APPENDIX C EQUIPMENT AND ANCILLARY SUPPLIES PROVIDE TO STUDY SITES

The following equipment/supplies will be supplied to an investigative site for the duration of the study provided that the site does not already have such equipment/supplies available for use. This information will be documented in the Clinical Trial Agreement, which indicates that the equipment and any remaining supplies are to be returned to JJSV at the completion of the study.

- M&S Technologies CTS-1000 Smart System[®] Computerized Vision Testing System, including laptop computer and tablet ("M&S System")
- Commercially-available standard fluorescein strips
- Commercially-available lissamine strips
- Tape measure (meters)
- Activator II

APPENDIX D MANUAL OF TESTING PROCEDURES

Biometry shall be measured with the optical biometry measurement system. The measurement results will be retained by the Investigator.

Biomicroscopic Slit Lamp Examination shall be performed via biomicroscopic slit-lamp exam for determination of medical findings including but not limited to the adnexa, conjunctiva, sclera, cornea, and iris.

Contrast Acuity Test: binocular, best corrected, photopic, 10% low contrast acuity and 20/40 contrast threshold test will be measured at the designated postoperative visits. Detailed instructions for contrast sensitivity testing are provided in **Appendix S**.

Corneal Topography shall be measured with a corneal topography system, e.g. the iDesign System (preferred), a Scheimpflug (Pentacam), or Placido (Humphrey) disk-based system. Images will be retained by the Investigator.

Eyelid Margin Evaluation shall be performed preoperatively and postoperatively at designated visits. The Investigator or designee may use 10x to 16x magnification on the slit lamp biomicroscope to evaluate the eyelid appearance, or they may use digital ocular images of the eyelid gained through LipiView II, and grade the eyelid appearance, as defined in **Appendix J**.

Fundus Examination shall be performed with or without pharmacological pupil dilation. If mydriatic agents are used, then installation of mydriatic agents should be used at least 30 minutes prior to determining the status of the ocular media, retina and lens. Based on prior studies, the LipiFlow treatment is not expected to have any effect on the posterior segment and therefore, is not routinely assessed after treatment. However, dilated retinal examination will be performed at scheduled follow-up or unscheduled visits if needed to evaluate an ocular health problem under the physician's discretion.

Keratometry (not simulated K) shall be conducted preoperatively using an auto or manual keratometer. The same keratometry method is to be used at each required visit, e.g., if auto keratometry was recorded at the preoperative exam, all postoperative keratometry readings should be auto K's. Do not use "sim K" from the corneal topography unit.

Lighting levels and lane calibration will be assessed by a representative of the Sponsor to ensure the lane length and lighting conditions are consistent across sites. The site or Sponsor designee will verify the chart background luminance level of 85 cd/m² (80-110 cd/m² acceptable) prior to use of the measurement device.

Manifest Refraction is to be performed under photopic conditions (85 cd/m², 80-110 cd/m² acceptable) using either the phoropter or trials frames and the M&S System. Manifest refraction is to be performed using the Maximum Plus refraction method as detailed in **Appendix M**. Because 4.0 meters is not optical infinity, a refraction adjustment of +0.25 D sphere must be used when performing uncorrected distance visual acuities. **Appendix N** lists the refraction adjustments.

Meibomian Gland Assessment is used to evaluate meibomian gland function. It is used to determine study eligibility based on total meibomian gland secretion score of 15 or less (on a scale of 0 to 45) for each eye at Baseline Visit. The Meibomian Gland Assessment is to be administered preoperatively and at designated postoperative study exams, as defined in **Appendix G**.

Meibomian Gland Imaging through LipiScan or LipiView II will be taken preoperatively and at designated postoperative study visits. LipiScan or LipiView II system will be used to capture, archive, and store the digital images of Meibomian glands of upper and lower eyelids in each eye, as defined in **Appendix I**.

Ocular Surface Staining of the cornea and conjunctiva is evaluated preoperatively and at the designated study visits. The Investigator or designee assesses the corneal staining after instillation of fluorescein dye in the eye, and assesses the conjunctival staining after instillation of lissamine green dye in the eye, as defined in **Appendix H**.

Ocular/Visual Symptom Assessment: The subjective ocular symptoms are to be assessed at the designated visit by asking “Are you having any difficulties with your eyes/vision?” Subjects should not be prompted for specific responses.

PRVSQ questionnaire: Patient-Reported Visual Symptom Questionnaire (PRSVQ) will be used for the assessment. It is a directed questionnaire intended to collect information on visual symptoms. In order to minimize any effect of the doctor-patient relationship may have on a subject’s responses on the questionnaire, the study questionnaires will be self-administered by the subjects. The PRVSQ is to be administered at the start of the preoperative visits and at every follow-up visit, prior to any visual acuity testing.

SPEED Questionnaire is a self-administered, validated assessment tool designed specifically to assess frequency and severity of dry eye symptom. It is used to determine study eligibility based on none to mild dry eye symptoms at Baseline Visit and to evaluate ocular comfort at Baseline and follow-up visits. Dry eye symptoms assessed using the SPEED questionnaire are dryness, grittiness or scratchiness; soreness or irritation; burning or watering; and eye fatigue. The SPEED questionnaire is to be administered preoperatively and at designated postoperative study exams, as defined in **Appendix K**.

Tear Break-Up Time (TBUT) is measured preoperatively and at designated postoperative study exams. Three separate measurements of tear break-up time are taken for each eye using a stopwatch to record the time. For data analysis, the three measurements are averaged to represent the mean tear break-up time for each eye. The Investigator or designee measures tear break-up time under a slit-lamp biomicroscope following instillation of fluorescein dye in the eye using the Dry Eye Test (DET) method, as defined in **Appendix L**.

APPENDIX E INSTRUCTIONS FOR EYELID MARGIN CLEANING

The lower lid margins including the area directly over the meibomian gland orifices are cleaned to remove accumulated devitalized cellular material cell and other products that build up along the lid margin in patients with MGD. Prior research has shown that cleaning the lid margin surface can decrease dry eye symptoms and increase meibomian gland function.^{xxiii} Performing lid margin cleaning prior to a LipiFlow treatment may aid in the treatment of MGD because cleaning the meibomian gland orifices and lid margin surface allows for optimal passage of the oil from the gland to the lid margin surface across the mucocutaneous junction and ultimately into the tear film.

The lid margin surface can be divided into three distinct sections: 1) the keratinized surface; 2) the Line of Marx (the stained devitalized surface cells of the mucocutaneous junction denoting the transition between the dry keratinized surface and the wet conjunctival surface); and 3) the conjunctival surface. A healthy keratinized surface has minimal debris, readily visible and uncapped meibomian gland orifices, minimal telangiectasia, and no lid margin irregularities such as lid notching or other findings indicating significant tissue change, as noted on the left in **Figure 1**. Conversely, the majority of MGD patients exhibit tissue changes (e.g. meibomian gland capping) and build-up of material on the keratinized lid margin surface. These changes and accumulated material are readily observed with the slit lamp, as shown on the right in **Figure 1**.

Figure 1: Examples of a healthy lid margin keratinized surface (left) and an abnormal lid margin surface with capped glands and accumulation of debris (right)

The Line of Marx cannot be easily visualized without staining. The accumulated devitalized cells of the Line of Marx are readily observed using lissamine green dye, white light and the slit lamp. A thin staining, slightly elevated Line of Marx that runs parallel to the lid margin and does not undulate is considered normal, as shown on the left in **Figure 2**. As loss of meibomian gland function progresses, the Line of Marx becomes thicker both in height and width, begins to undulate, and finally advances

anteriorly towards the lash line, as shown on the right in **Figure 2**.^{xxiv,xxv} Elevation and thickening of the Line of Marx is very common in patients with MGD and occurs in the vast majority of all adults over age 30. With progression of chronic MGD, the Line of Marx advances over the meibomian gland orifices such that the orifices open up onto wet conjunctival surface as opposed to the intended dry keratinized surface. As a result of the changes in the position, thickness and height of the Line of Marx, the delivery of oil from the gland orifices to the tear film is altered.

[figure not shown]

Figure 2: Examples of a healthy stained Line of Marx (left) and an abnormal Line of Marx with thickening, antero-placement and undulation (right)

The Investigator or designee uses the following procedure and a commercially available golf club spud (**Figure 3**) to clean the lid margin surface of the lower eyelids. First, the Line of Marx is cleaned followed by the keratinized lid surface. The wet conjunctival surface is not cleaned. In addition, the upper eyelid margins are not cleaned.

Figure 3: Golf Club Spud (Hilco Wilson Ophthalmics; Plainville, MA)

NOTE: The lid margin cleaning procedure is performed without anesthetic and is not intended to remove tissue that cannot be removed with gentle motion and mild pressure of the golf club spud. The patient should not experience discomfort, and there should be no tissue damage evident after the procedure is complete. No post procedure application of topical medications should be necessary.

Procedure for Cleaning the Line of Marx (the lissamine green stained cells on the surface of the mucocutaneous junction): The goal of the cleaning is to remove the lissamine green stained cells from the Line of Marx.

1. With the patient comfortably seated at the slit lamp (16x magnification with white light), gently evert the lower eyelid.
2. Ask the patient to look up.

3. Stain the conjunctiva and lid margin with lissamine green dye so that the Line of Marx is clearly visible.
4. Place the golf club spud (**Figure 3**) onto the lid margin directly over the Line of Marx.
5. Gently maneuver the golf club spud laterally (nasal to temporal or vice versa) in small wiping motions with mild pressure across the entire length of the Line of Marx, as shown in **Figure 4**.

Figure 4: Cleaning the Line of Marx with a Golf Club Spud

6. Adjust the pressure applied to the lid margin as needed based on individual morphology and resistance of the tissue, while monitoring the removal of the lissamine green stained cells. The patient should be comfortable during the procedure. Any discomfort is an indication that the pressure applied needs to be adjusted.
7. After the cleaning of the Line of Marx is complete, verify that few to no stained cells are still visible along the Line of Marx.
8. Repeat steps 1 to 7 for the other eye.

Procedure for Cleaning the Keratinized Lid Surface: The goal of the cleaning is to remove any accumulated debris on the keratinized lid margin and any accumulated material potentially obstructing the meibomian gland orifices.

1. With the patient comfortably seated at the slit lamp (16x magnification with white light), gently evert the lower eyelid.
2. Ask the patient to look up.
3. Place the golf club spud (**Figure 3**) onto the keratinized lid margin with the tip of the spud placed at the edge of the Line of Marx, which was previously cleaned.
4. Gently maneuver the golf club spud laterally (nasal to temporal or vice versa) in small wiping motions with mild pressure across the entire keratinized lid margin surface covering all areas from the edge of the Line of Marx to the base of the lashes at the lash line.
5. Adjust the pressure applied to the lid margin as needed. The patient should be comfortable during the procedure. Any discomfort is an indication that the pressure applied needs to be adjusted.

6. After the cleaning of the keratinized lid margin is complete, verify that little to no sheen is visible on the lid margin surface and any functional meibomian gland orifices are exposed. Narrow furrows or striations, which run perpendicular to the lid margin, may also be observed.
7. Repeat steps 1 to 6 for the other eye.

